One of the most effective arms of the human immune system is the ability of very low concentrations of antibody proteins to bind to viruses, bacteria and toxins and "neutralise" their activity or ability to infect. In contrast to cellular immunity, which may cause tissue destruction and pathology, antibody-mediated immunity can be very passive, while completely preventing infection. How antibodies bind their targets varies enormously, ranging from unhelpful "blocking" antibodies or narrowly focussed neutralising antibodies, to highly protective "broadly neutralising" antibodies (bNAbs) that can neutralise a wide range of strains of the same pathogen. Such bNAbs are especially sought after in virus infections such as HIV, influenza and others where the virus mutates to evade immune responses that are too narrow or focussed. Antibodies arise when an "immunogen" (an immunogen is anything that induces an immune response, typically a foreign protein) is taken up by the immune system and shown to white blood cells – T and B cells - by specialised immune cells. In some cases the T and B cells bind the immunogens to receptors on their surface, triggering an immune response in which T cells "help" B cells to manufacture specific antibodies. The events around how the protein is processed into manageable pieces, shown to the T and B cells, and the pattern of chemical signals produced by the immune cells is highly complex, but eventually determines how broad the antibody response will be (its breadth). For infections like HIV and influenza, decades of research and clinical vaccine trials have had limited or no success. To take HIV as an example, we have an almost complete lack of understanding of how immunogens interact with the naive human B cell receptor (BCR) repertoire and the pathways required to induce bNAbs during an infection or after an immunisation. Animal models have failed as the naïve, germline encoded, B cell antibody receptor repertoires of non-human species are sufficiently different from those of humans to render design and selection of vaccines based on non-human species problematic. Additionally, bNAbs isolated from HIV-1-infected individuals have structural features that occur rarely or not at all in other mammals, such as unusually long loop-binding regions (CDRH3 loops) required to penetrate past glycans on the surface of the envelope spike that shield key neutralising epitopes (Mascola JR 2013). There is therefore a critical need to better understand, in human experimental medicine models of immune challenge, how immunogens and B/T cells interact in the development of protective bNAb anti-viral responses.

Our approach to resolving this impasse is to challenge the human immune system with rationally-designed model immunogens to determine the structural and other characteristics required to drive human B cell antibody responses towards neutralisation breadth. We have selected HIV as an experimental model as there is a reasonable understanding about the specificity and function of anti-HIV bNAbs, as well as an urgent need to identify novel immunisation approaches following decades of failed or poorly successful trials. There is also a huge database of safety using HIV proteins as immunogens, and the technological expertise to design and manufacture HIV viral proteins. Assays for HIV neutralising activity are also well established in our laboratories. Although focussed on HIV, our findings will be applicable to other viral infections.

The model immunogens we propose to use in these experimental medicine studies are unlikely to be suitable as vaccines, and any clinical development would require iterative cycles of design refinement and development based on immunological insights gleaned from these experimental investigations. Therefore, the focus is on in-depth characterisation of the elicited immune response to rationally-designed model immunogens that may inform the design process of actual vaccines. This experimental medicine approach is only now possible due to unprecedented progress in our abilities to study the human immune system and to obtain complete information on immune responses to vaccination, since performing research on the human immune system is now almost as easy as it has been in mice. The main focus of this study will be to determine which of the design strategies is able to prime human germline (naive) B cells and drive antibody responses towards induction of neutralising antibody breadth.

Our range of model immunogens will be based on the envelope (Env) glycoprotein of HIV-1, which is the only target of neutralising antibodies, and therefore the only virally-encoded immunogen relevant for induction of such antibodies by immunisation. To ensure reproducibility of results and the highest level of volunteer safety, all immunogens will be manufactured under cGMP, using techniques applied to vaccine immunogens.

Env has extensive amino acid variation, structural and conformational instability, and immunodominance of hypervariable regions (Kwong PD, 2011; Sattentau QJ, 2013). We will design soluble immunogens that closely mimic the native viral trimer *in situ*, but that incorporate design strategies that may alter the intrinsic viral immune evasion mechanisms (Sanders RW, 2013). Env is made up of three identical complexes (trimers) each of which contains two molecules, gp120 and gp41 that can be modified to make a soluble molecule called gp140, upon which our immunogens are based. We have developed model consensus gp140 Env trimers (consensus of all global strains) designed to prime B cell responses to common epitopes represented in all HIV-1 subtypes. We have utilised two design strategies to stabilise these in a native-like conformation: ConM SOSIP and ConS UFO. The ConM SOSIP trimer includes novel mutations that include the incorporation of a disulphide linkage between the gp120 and gp41 ectodomain (making up gp140) which prevents their disassociation into monomer subunits.

The ConS UFO includes a short flexible amino-acid linker to tether the gp120 and gp41 subunits together as an alternative strategy to prevent dissociation of the Env trimer. We wish to test both designs to determine the effect on B cell repertoire. To further stabilize global architecture we will employ an EDC crosslinking approach that has been shown to conserve bNAb epitopes, reduce non-antiviral antibody responses, and enhance overall immunogen stability (Schiffner et al., 2015). Thus, in Part 1 of this study we will test EDC ConM SOSIP and EDC ConS UFO versions in parallel.

A critical adjunct to our consensus-based model design is to use cocktails of mosaic gp140 Env trimers designed to overcome the immunodominance of hypervariable regions of Env and to determine whether they will focus antibody responses towards conserved neutralisation epitopes. While designed using computer algorithms, these mosaics represent authentic Env

structures that are fully functional and native in their conformation. Our novel designs aim to eliminate unwanted immunodominant antibody responses and focus B cells towards highly conserved supersites of vulnerability on Env, with particular emphasis on quaternary bNAb epitopes (Julien, JP, 2013; Kong L, 2013; Lyumkis D, 2013). Like the ConM SOPSIP and ConS UFO trimers described above, the mosaic trimers have disulphide linkage which prevents disassociation of gp120 and gp41 into monomer subunits.

In Groups A–E of this study, we will prime with one of the consensus immunogens (ConM or ConS), and boost with a cocktail of two mosaic immunogens (Mos3.1 and Mos3.2).

In Groups F–I of this study, we will explore the use of three mosaic immunogens (Mos3.1, Mos3.2 and Mos3.3) used sequentially (in a series of different orders), or as a cocktail, to focus B cell responses towards conserved areas of Env. To amplify these responses we intend to give a final boosting immunization with both consensus immunogens (ConM and ConS).

In Groups J–M we will use two HIV-1 envelope sequences (AMCO11 and 763 SOSIP) which the EAVI2020 programme has found to be associated with the early induction of broadly neutralising antibodies. The sequences were identified from two HIV infected individuals that displayed HIV neutralisation breadth early in infection (less than 12 months). This is unusual as typically neutralisation breadth is only seen to develop in <5% of subjects and only after a period of more than 2 years. We seek to test the hypothesis that these two envelope sequences may display unique potential to prime and/or drive the induction of broadly neutralising antibody responses in HIV negative healthy volunteers. To test this hypothesis the EAVI2020 consortium has manufactured stabilised versions of these two envelope proteins to GMP. These will be used alone and in various combinations with consensus and mosaic immunogens to determine the extent to which they can drive the induction of broadly neutralising antibodies. Responses to these unique envelope sequences will be compared and contrasted to the consensus and mosaic immunogens evaluated in Groups A–I.

The extent to which these different strategies may induce neutralising breadth, and the identification of the mechanisms and drivers involved, can only be determined empirically through human immunogen challenge studies. The results from these studies will help inform the future direction of additional refinement of HIV vaccine strategies for the induction of protective antibodies.

Objectives

The objective of this experimental medicine study is to determine the extent to which different prime-boost combinations influence serum neutralising antibody breadth and associated B and T cells responses.

We hypothesise that the different prime-boost model immunogen combinations will have differential impact on:

a) the magnitude and breadth of induced serum neutralising antibodies;

and

b) the induced B- and T-cell responses in peripheral blood

We will investigate this by challenging the immune system of healthy adults with various model immunogens based on HIV-1 Env (ConM and ConS, with and without EDC stabilisation; Mos3.1, Mos3.2 and Mos3.3, and AMC011 and 763 SOSIP) in different prime-boost combinations.

In Groups A–I we will investigate the impact of a later immunisation challenge with either consensus or mosaic gp140 Envs to determine any additional effect on breadth of antibody neutralisation.

The primary outcome will be measurement of specific viral neutralisation activity of serum antibodies. Exploratory outcomes will include titres of binding antibodies in serum and the characterisation of blood B and T cell responses.

Data derived from these studies will help to inform how the structure of rationally-designed immunogens drives the immune system towards developing broadly neutralising antibodies that are rarely induced under natural conditions.

Primary Outcomes

- Serum titres of neutralising antibodies to virus expressing ConM and ConS envelopes
- Serum titres of neutralising antibodies to virus expressing Mosaic envelopes (Mos3.1, Mos3.2 and Mos3.3)
- Serum titres of neutralising antibodies to virus expressing AMC011 and 763 SOSIP envelopes

Exploratory Outcomes

• These will include: measurement of binding antibodies in serum; assessment of neutralisation breadth using a wider panel of globally circulating HIV strains; measurement of serum antibody function (ADCC, ADCP, FcR dimer binding); measurement of the magnitude and phenotype of B cell (plasmablast and memory B cells) and T cell responses (CD4 and CD8) in peripheral blood mononuclear cells (PBMC). Some endpoints will include only a subset of enrolled volunteers. Paxgene tubes for blood transcriptomics will be collected only from group A (see Table 2) because it is not expected that responses will differ at this level between groups. Blood transcriptomic profiles induced by immunisation will be correlated with the magnitude of induced serum antibody response.

Fine needle aspiration

- In addition, the feasibility and safety of lymph node aspiration will be explored, and immunogen induced germinal centre B and T cell responses will be assessed, in volunteers from groups B-M willing to attend additional visits to have an ultrasound guided fine needle lymph node aspiration from axillary, cervical or inguinal lymph nodes. Fine needle aspiration biopsies will occur in line with the sub-study protocol in Appendix 1.
- This will be optional and participants will be provided with a separate fine needle aspiration information sheet and consent form. The participants will be reviewed by the medical team for any contraindications to fine needle aspiration prior to the procedure being carried out.
- An additional blood sample of 42 ml of peripheral blood will be collected at each fine needle aspiration visit to compare the T- and B-cell populations by flow cytometry and to compare serum neutralising antibody activity.

Statistics and Sample Size

It is difficult to give an estimate of the power of group comparisons using quantitative antibody titre outcomes at this stage as this is dependent on the number of responders, and the large number of experimental parameters in this experimental study. The sample size is based on the previous studies of HIV-1 gp140 immunogens (Joseph S, 2017, Cosgrove CA, 2016, Kratochvil S, 2017, Lewis DJ, 2011). It is not the remit of this exploratory study to recruit a sufficient number of volunteers to be statistically confident about the differences between groups. By the end of this study, 8–10 volunteers will have been exposed to each schedule and this provides confidence around the response/event proportions of 0–100% in Table 1.

Table 1: Sample Size

Number of "responders"	mber of "responders" Proportion if n=10							
		interval ¹						
0	0%	0 – 31%						
2	20%	3 – 56%						
4	40%	12 – 74%						
6	60%	26 – 88%						
8	80%	44 – 98%						
10	100%	69 – 100%						
Number of	Proportion if n=8	95% confidence						
"responders"		interval ²						
0	0%	0–32%						
1	12.5%	2–47%						
2	25%	7–59%						
3	37.5%	14–69%						
4	50%	22–78%						

5	62.5%	31–86%
6	75%	41–93%
8	100%	68–100%

^{1, 2} Clopper-Pearson or Wilson method (suitable for small sample sizes)

Number (percent) of responders, and median [IQR] and mean (range) of titre responses will be tabulated by group. Group comparisons of titre levels will be conducted via Kruskal-Wallis test or Wilson method suitable for small sample sizes.

Volunteers & Withdrawal Criteria

We will recruit 114 healthy male and females adults into five groups of 10 each (A-E) and eight groups of 8 each (F–M), see Table 2. Recruitment will select potential volunteers who are willing to undergo serial blood draws. Health status will be determined at screening which will comprise a medical history, symptom-directed physical examination, vital signs, urine pregnancy test (women only), HIV screen, and routine safety blood draws (full blood count; renal, liver and bone panels).

Additional volunteers may be enrolled to replace early withdrawals. The reason(s) for withdrawal will be recorded in volunteer's files.

All volunteers are free to withdraw from the study at any time, for any reason, without affecting their future medical care. The PI may decide to withdraw a volunteer if the investigator deems that continuing might compromise the volunteer's wellbeing or interfere with the achievement of the study's objectives.

Table 2: Schedule of immunisations and doses of model immunogens

			Month:	5							
Group	N	0	0 3 6								
			Part 1		Part 2						
Α	10	ConM SOSIP	ConM SOSIP	Mos3.1 + Mos3.2							
		100 μg	100 μg	100 µg	100ug (2x50ug)						
В	10	EDC ConM SOSIP	EDC ConM SOSIP	EDC ConM SOSIP	Mos3.1 + Mos3.2						
		100 μg	100 μg	100 µg	100ug (2x50ug)						
С	10	ConS UFO	ConS UFO	ConS UFO	Mos3.1 + Mos3.2						
		100 μg	100 μg	100 µg	100ug (2x50ug)						
D	10	EDC ConS UFO	EDC ConS UFO	EDC ConS UFO	Mos3.1 + Mos3.2						
		100 μg	100 μg	100 µg	100ug (2x50ug)						
E	10	ConS UFO	ConS UFO	ConM SOSIP	Mos3.1 + Mos3.2						
		100 μg	100 μg	100 μg 100 μg							
			Month								
Group	N	0	2	6							
			Part 1		Part 2						

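### Table 1 uses Clopper-Pearson limits for n=10 and Wilson limits for n=8, so the smaller groups look more precise at mid-range; one upper limit is also misrounded

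*Protocol*

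**What the plan says.** The protocol section Statistics and Sample Size declines to state power: "It is difficult to give an estimate of the power of group comparisons using quantitative antibody titre outcomes at this stage". It says that "The sample size is based on the previous studies of HIV-1 gp140 immunogens", and then turns to precision: "8–10 volunteers will have been exposed to each schedule and this provides confidence around the response/event proportions of 0–100% in Table 1".

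Table 1 has two stacked blocks. The n=10 block carries superscript 1 on its interval column and the n=8 block carries superscript 2. One footnote serves both markers: "Clopper-Pearson or Wilson method (suitable for small sample sizes)".

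Under Volunteers & Withdrawal Criteria the groups are "five groups of 10 each (A-E) and eight groups of 8 each (F–M)". That makes 5 × 10 + 8 × 8 = 114 volunteers, of whom 64, in eight of the 13 groups, fall under the n=8 block.

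**The concern.** At a given response proportion and with one method, fewer volunteers must give a wider interval, and the width is greatest at 50%. The 4/8 row should therefore be the widest in the table, yet it is printed narrower than 4/10 and 6/10. That ordering suggests that the two blocks were computed differently.

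What is at stake is the stated precision. A reader who compares the blocks would conclude that going from 10 to 8 per group costs almost nothing at 0% and 100% and gains precision in the middle. Both conclusions would be false, and the protocol has no other figure to correct them.

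**Working it through.** **Inputs.** Two-sided 95% level, n=10 and n=8, and the responder counts x printed in Table 1.

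**Formulas.**
- Clopper-Pearson: lower limit = 2.5% quantile of Beta(x, n−x+1); upper limit = 97.5% quantile of Beta(x+1, n−x).
- Wilson, with z = 1.96 and z² = 3.8416: (x + z²/2)/(n + z²) ± [z/(n + z²)] × √[x(n−x)/n + z²/4].

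Worked case, Wilson 4/8: the centre is (4 + 1.9208)/11.8416 = 0.500. The half-width is (1.96/11.8416) × √(2 + 0.9604) = 0.1655 × 1.7206 = 0.285. This gives 21.5–78.5%, printed as 22–78%.

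**All printed rows (in %).**

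| Row | Printed | Clopper-Pearson | Wilson |
|---|---|---|---|
| 0/10 | 0–31 | 0–30.85 | 0–27.75 |
| 2/10 | 3–56 | 2.52–55.61 | 5.67–50.98 |
| 4/10 | 12–74 | 12.16–73.76 | 16.82–68.73 |
| 6/10 | 26–88 | 26.24–87.84 | 31.27–83.18 |
| 8/10 | 44–98 | 44.39–97.48 | 49.02–94.33 |
| 10/10 | 69–100 | 69.15–100 | 72.25–100 |
| 0/8 | 0–32 | 0–36.94 | 0–32.44 |
| 1/8 | 2–47 | 0.32–52.65 | 2.24–47.09 |
| 2/8 | 7–59 | 3.19–65.09 | 7.15–59.07 |
| 3/8 | 14–69 | 8.52–75.51 | 13.68–69.43 |
| 4/8 | 22–78 | 15.70–84.30 | 21.52–78.48 |
| 5/8 | 31–86 | 24.49–91.48 | 30.57–86.32 |
| 6/8 | 41–93 | 34.91–96.81 | 40.93–92.85 |
| 8/8 | 68–100 | 63.06–100 | 67.56–100 |

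In the n=10 block, 11 of the 12 limits are Clopper-Pearson and no row matches Wilson. In the n=8 block, all 16 limits are Wilson and no row matches Clopper-Pearson. Agresti-Coull, Jeffreys and Wald intervals reproduce neither block.

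**The exception.** The 8/10 upper limit is 97.48%, which rounds to 97, not 98. The table shows this itself: 2/10 is printed as 3–56%, and its mirror image is 100−56 to 100−3, that is 44–97%.

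**Widths (percentage points).**

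| Row | As printed | Clopper-Pearson | Wilson |
|---|---|---|---|
| 4/8 | 56 | 68.6 | 57.0 |
| 3/8 and 5/8 | 55 | 67.0 | 55.7 |
| 4/10 and 6/10 | 62 | 61.6 | 51.9 |
| 5/10 (not printed) | – | 62.6 | 52.7 |
| 0/8 and 8/8 | 32 | 36.9 | 32.4 |
| 0/10 and 10/10 | 31 | 30.8 | 27.8 |

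As printed, 4/8 is 62 − 56 = 6 points narrower than 4/10. Under one method it is wider, by 68.6 − 61.6 = 7.0 points (Clopper-Pearson) or 57.0 − 51.9 = 5.1 points (Wilson). At 0% and 100% the printed cost of the smaller group is 32 − 31 = 1 point. It should be 36.94 − 30.85 = 6.1 points (Clopper-Pearson) or 32.44 − 27.75 = 4.7 points (Wilson).

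**The case against.** The best defence is that the footnote discloses the mix. It has two markers and two methods, listed in the order that the recomputation confirms, so reading it as *respectively* makes the assignment correct. Both methods are standard for small samples, and every interval but one is valid under its own method.

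The protocol also never compares the two blocks. The only proportions they share are 0% and 100%, where n=8 is printed as the wider, and the reversal appears only when a reader subtracts limits. The sample size is attributed to earlier studies, the primary outcomes are titres, and the protocol prespecifies no responder interval. Under either method the message is that precision is low.

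Much of this stands. No design decision depends on the table, and the rounding slip alone is trivial. But the footnote says *or*, does not assign a method to either block, and gives no warning that widths cannot be compared across them. Even the generous reading leaves the blocks non-comparable and one limit wrong. Nor is this detail that can wait for the SAP, because the figures are already printed in the protocol.

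**Conclusion.** The concern holds. Table 1 mixes Clopper-Pearson (n=10) with Wilson (n=8). This reverses the mid-range ordering of precision between the two group sizes and understates the loss at 0% and 100% (1 point printed, against 6.1 or 4.7). The 8/10 upper limit is 1 point too high.

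The consequence is limited to the stated precision for eight of 13 groups. The sample size and the titre-based primary outcomes do not change. The point matters enough to correct because no power is given and this table alone quantifies what 8 to 10 volunteers per schedule provide. The result rests only on the printed counts and the two-sided 95% level. It does not depend on which of the two methods the sponsor prefers.

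**What to change.** Choose one method, apply it to both blocks and name it in the footnote without *or*.

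- **Clopper-Pearson throughout:** the n=8 rows become 0: 0–37; 1: 0–53; 2: 3–65; 3: 9–76; 4: 16–84; 5: 24–91; 6: 35–97; 8: 63–100%. Correct 8/10 to 44–97%.
- **Wilson throughout:** the n=10 rows become 0: 0–28; 2: 6–51; 4: 17–69; 6: 31–83; 8: 49–94; 10: 72–100%.

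If responder intervals are later reported, use the same method for every group.

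The cost is one block of figures and one reworded footnote. With Clopper-Pearson the n=8 intervals become about 5 to 12 points wider per row (for example 32.4 to 36.9 at 0/8 and 57.0 to 68.6 at 4/8), which is less favourable but consistent with the method already used for n=10. Enrolment and the primary analysis stay as they are.

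### The Wilson method is offered for comparing titre levels between groups, but it is an interval for a single responder proportion and uses no titre values

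*Protocol*

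**What the plan says.** All three primary outcomes in the protocol are serum neutralising titres against different envelopes, the first being "Serum titres of neutralising antibodies to virus expressing ConM and ConS envelopes". The Statistics and Sample Size section treats these as continuous-type data when it speaks of "the power of group comparisons using quantitative antibody titre outcomes".

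The analysis is stated in two sentences below Table 1. The first covers description: "Number (percent) of responders, and median [IQR] and mean (range) of titre responses will be tabulated by group". The second covers comparison: "Group comparisons of titre levels will be conducted via Kruskal-Wallis test or Wilson method suitable for small sample sizes". No other sentence in the protocol says how titres will be compared, and no rule is given for choosing between the two methods.

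The Wilson method is mentioned in one other place, the Table 1 footnote: "Clopper-Pearson or Wilson method (suitable for small sample sizes". The text introducing that table says what the intervals are for: "8–10 volunteers will have been exposed to each schedule and this provides confidence around the response/event proportions of 0–100% in Table 1".

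**The concern.** The comparison sentence offers two alternatives for the same task. Kruskal-Wallis is a rank test of a quantitative or ordinal outcome across groups and suits titres. The Wilson method, as this protocol uses it, is a confidence interval for a binomial proportion in one group. It answers how precisely a responder rate is known. It does not address whether titres differ between schedules.

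The objectives include the magnitude of the induced neutralising antibodies as well as their breadth. A method that sees only responder counts cannot address magnitude. If an analyst took the second option literally, the primary outcome would be reduced to a responder rate, and the comparison would become an informal reading of intervals side by side. A later analysis plan that follows the protocol must either repeat the error or depart from it.

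**Working it through.** **Step 1. Which method produced Table 1?** Inputs: the printed responder counts, n=8 and n=10, and the 95% level (z=1.96, z²=3.8415).

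Wilson limits, with p = x/n:

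(p + z²/2n ± z·√[p(1−p)/n + z²/4n²]) / (1 + z²/n)

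Clopper-Pearson lower limit: the 2.5% point of Beta(x, n−x+1). Upper limit: the 97.5% point of Beta(x+1, n−x). The limits are 0 and 1 at the extremes.

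Worked examples for n=8:
- 0/8, Wilson upper limit: z²/(n+z²) = 3.8415/11.8415 = 32.4%.
- 8/8, Wilson lower limit: n/(n+z²) = 8/11.8415 = 67.6%.
- 8/8, Clopper-Pearson lower limit: 0.025^(1/8) = 63.1%.

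| Responders | Printed (%) | Wilson (%) | Clopper-Pearson (%) |
|---|---|---|---|
| 0/8 | 0–32 | 0–32.4 | 0–36.9 |
| 1/8 | 2–47 | 2.2–47.1 | 0.3–52.7 |
| 2/8 | 7–59 | 7.1–59.1 | 3.2–65.1 |
| 3/8 | 14–69 | 13.7–69.4 | 8.5–75.5 |
| 4/8 | 22–78 | 21.5–78.5 | 15.7–84.3 |
| 5/8 | 31–86 | 30.6–86.3 | 24.5–91.5 |
| 6/8 | 41–93 | 40.9–92.9 | 34.9–96.8 |
| 8/8 | 68–100 | 67.6–100 | 63.1–100 |
| 0/10 | 0–31 | 0–27.8 | 0–30.8 |
| 2/10 | 3–56 | 5.7–51.0 | 2.5–55.6 |
| 4/10 | 12–74 | 16.8–68.7 | 12.2–73.8 |
| 6/10 | 26–88 | 31.3–83.2 | 26.2–87.8 |
| 8/10 | 44–98 | 49.0–94.3 | 44.4–97.5 |
| 10/10 | 69–100 | 72.2–100 | 69.2–100 |

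The n=8 block is Wilson throughout, with every limit within 0.48 points. The largest gap to Clopper-Pearson in each row is 4.9 to 6.5 points. The n=10 block is Clopper-Pearson, within 0.52 points. Its largest gap is the upper limit for 8/10, which computes to 97.48 and is printed as 98.

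So the Wilson method in this document has two inputs, x and n, from a single group.

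**Step 2. What does it report when titres differ?** Take two equal groups in which every volunteer responds. Assume no tied titres and use the chi-square approximation for Kruskal-Wallis:

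H = 12/[N(N+1)] · Σ(Rᵢ²/nᵢ) − 3(N+1)

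- 8 v 8, balanced ranks (68 and 68): H = 12/272 × (578 + 578) − 51 = 0, p = 1.00.
- 8 v 8, no overlap (36 and 100): H = 12/272 × (162 + 1250) − 51 = 11.29, p = 0.0008.
- 10 v 10, balanced ranks (105 and 105): H = 12/420 × (1102.5 + 1102.5) − 63 = 0, p = 1.00.
- 10 v 10, no overlap (55 and 155): H = 12/420 × (302.5 + 2402.5) − 63 = 14.29, p = 0.0002.

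The Wilson interval does not move: 67.6–100% in both groups of 8 and 72.2–100% in both groups of 10 (10/13.8415 = 72.2%). It is the same under full agreement and under complete separation.

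**The case against.** The strongest reply is that this is an editing slip with little consequence. A valid test stands first in the same sentence. The misnamed option cannot be run on titres, so it is hard to see it yielding a wrong titre analysis. No sample size, power figure or decision rule depends on it. The protocol also says it does not aim to recruit enough volunteers "to be statistically confident about the differences between groups". The wording after the method's name nearly repeats the Table 1 footnote, which suggests it was carried over. Another rank test may also have been meant; the document does not settle which. All of this stands, and it limits the weight of the point. It does not make the sentence correct.

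The illustration can also be challenged. Universal response may be unrealistic, since the protocol reports very limited neutralisation from earlier native gp140 studies at this dose. The p-values are approximations: under complete separation the exact two-sided values are 2/12870 = 0.00016 (8 v 8) and 2/184756 = 0.00001 (10 v 10). Where many volunteers do not respond, Kruskal-Wallis also separates groups less well. In an assumed example with four of eight responding in each group, non-responders tied at 20 and responders' titres ten times higher in one group, H = 0.81 and p = 0.37. These remarks are fair, but the argument does not depend on the p-values. For any equal responder count the two Wilson intervals are identical whatever the titres; in that last example both are 21.5–78.5%.

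A Wilson-type interval for a difference between two proportions would not rescue the sentence, because it would still compare responder rates.

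Nor is this a detail that can wait for the analysis plan. The protocol does not leave the method open; it names one that cannot perform the stated task.

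**Conclusion.** The concern holds. The only sentence on how the primary outcome is compared between groups names, as one of two options, a method that uses no titre values and makes no comparison. This follows from the protocol's own Table 1 and needs no assumption about the titre distribution. The Kruskal-Wallis figures in the working are illustrative and assume equal groups, all volunteers responding and no ties.

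The error is one of wording, not of design. Kruskal-Wallis remains valid, the Table 1 values can stand, and the exploratory aim limits the consequence. It is worth correcting because of where it sits and how little the correction costs.

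**What to change.** Ask the sponsor to confirm what was meant, and replace the comparison sentence with two sentences, for example:

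> Titre levels will be compared between groups by the Kruskal-Wallis test (Wilcoxon rank-sum test for two groups). Responder proportions will be reported by group with Wilson or Clopper-Pearson 95% confidence intervals.

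The rank-sum test is the two-group form of Kruskal-Wallis, so naming it adds no new method in substance. The wording works whether the phrase came from the footnote or was a slip for another rank test.

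Optionally, label the n=10 block of Table 1 as Clopper-Pearson and the n=8 block as Wilson. The widths of the two blocks are not directly comparable: 0/8 is 0–32% by Wilson and would be 0–37% by Clopper-Pearson.

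Cost: one sentence reworded and one added. No recalculation, data or volunteers are needed.
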